A Research Specialist (RS) from the Department of Anesthesiology and Perioperative Medicine will be assigned to the study who will provide data management support. The responsibilities of the RS include project compliance, data collection, abstraction and entry, data reporting, IRB correspondence, problem resolution and prioritization and coordination of the protocol study team activities. The data collected for this study will be entered into a secure departmental server. Source documentation and regulatory binders will be stored in a locked filing cabinet within a locked department office space. These sites are exclusively used for research documents and only members of the research team will have access to files for this study.

Quality Assurance

Registration reports will be generated every 6 months to monitor patient accrual and completeness of registration data. Routine data quality reports will be generated to assess missing data and inconsistencies. Accrual rates, and extent and accuracy of evaluations will be monitored throughout the study period. Potential problems will be brought to the attention of the study team for discussion and action.

Data and Safety Monitoring

The plans address the policies set forth by the NCI in the document entitled "Policy of the National Cancer Institute for Data and Safety Monitoring of Clinical trials" which can be found at <http://cancertrials.nci.nih.gov/researchers/dsm/index.html>. The MU Health Care Data and Safety Monitoring Plans can be found online.

There are several different mechanisms by which clinical trials are monitored for data, safety and quality. There are institutional processes in place for quality assurance (e.g., protocol monitoring, compliance and data verification audits, therapeutic response and staff education on clinical research QA) and departmental procedures for quality control, plus institutional committees that are responsible for monitoring the activities of the clinical trials program.

PROTECTION OF HUMAN SUBJECTS

Benefits and Risks

The experimental intervention (intravenous lidocaine infusion) is currently used at University of Missouri Hospital through the ERAS protocol. Numerous studies have shown significant patient benefits in all fields, including Urology. A review of 45, randomized studies demonstrated no major adverse events secondary to its usage. Therefore, we do not believe that the therapeutic aspects of this trial pose any risk different from patients undergoing robot assisted laparoscopic prostatectomy or a robot assisted laparoscopic partial nephrectomy.

Toxicities and side effects

Adverse outcomes are not anticipated with the doses of lidocaine being used in the protocol. Signs of lidocaine toxicity will be monitored per University Hospital standard of care protocol. This includes assessment and documentation by floor nursing staff, every 4 hours, of the signs and symptoms of lidocaine toxicity. The presence or lack of toxicity is reported in the medical record at these time points and pain nurse with the Department of Anesthesiology and Perioperative Medicine review this information. Management and review of medications will also be performed by the surgical and inpatient care teams per standard of care. Toxicity in our study will be evaluated clinically postoperatively by the presence of perioral paresthesia, metallic taste, tinnitus, confusion, agitation, muscle spasms, and seizures. Following standard of care, if there is concern of possible toxicity a lidocaine level may be ordered per standard of care.

Alternatives / Therapeutic options

The alternative to participation in the trial would be to undergo robot assisted laparoscopic prostatectomy or a robot assisted laparoscopic partial nephrectomy according to the surgeon's standard practice and not to participate in the study. No other aspect of patient care would differ.

Financial Costs and Burdens

Subjects will not be compensated for their participation and there are not costs involved in participation. Cost of the study medications, delivery from pharmacy, and administration will not be charged to the subject. The study is internally funded by the Department of Surgery – Urology Division and Department of Anesthesiology and Perioperative Medicine.

Privacy and Confidentiality

We will keep the study records confidential. No identifiers will be used in any reports or publications resulting from the study.

Volunteering Nature of the Study

Participation is entirely voluntary. All aspects of patient's care and monitoring will be unaffected by whether the patient chooses to consent for the study.

Serious Adverse Event (SAE) Reporting

Any SAE will be reported to the IRB as soon as possible, but no later than 5 calendar days. The reporting procedure will be followed as outlined in the University of Missouri protocol found in the “Core Standard Operating Procedure for Event Reporting.”.

INFORMED CONSENT PROCEDURES

Before protocol-specified procedures are carried out, consenting professionals will explain full details of the protocol and study procedures as well as the risks involved to participants prior to their inclusion in the study. Participants will also be informed that they are free to withdraw at any time. All participants must sign and date an IRB approved informed consent form indicating their consent to participate. This consent form meets the requirements of the Code of Federal Regulations and the Institutional Review Board.

Before any protocol-specific procedures can be carried out, the consenting professional will fully explain the aspects of patient privacy concerning research specific information. In addition to signing the IRB Informed consent, all patients must agree to the Research Authorization component of the informed consent form.

Each participant and consenting professional will sign the consent form. The participant will receive a copy of the signed informed consent form. A copy of the signed informed consent form will be placed in the participant’s chart and subsequently scanned into the electronic medical record under Research Consents.

REFERENCES

3. Centers for Disease Control and Prevention (CDC). Vital signs: overdoses of prescription opioid pain relievers--United States, 1999--2008. *MMWR Morb Mortal Wkly Rep.* 2011;60(43):1487-1492. <http://www.ncbi.nlm.nih.gov/pubmed/22048730>. Accessed May 25, 2018.

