This is a prospective, randomized, double-blinded, placebo-controlled clinical trial on lidocaine infusion for pain control and opioid consumption in patients undergoing either robotic-assisted laparoscopic prostatectomy or robotic-assisted laparoscopic partial nephrectomy at University of Missouri Hospital. Patients will be randomized in a 1:1 fashion and stratified by the type of surgery to receive a perioperative intravenous 0.8% lidocaine infusion at 1 mg/kg/h if $<$ age 65 and 0.5 mg/kg/h if \geq age 65 or an equal volume and rate of normal saline as a placebo. The infusion will be started 15 minutes after endotracheal intubation and continue for 24 hours.

After obtaining written consent, subjects will be randomized to receive lidocaine or normal saline. The anesthesiologist, surgeon, nurses, research staff, and patient will be blinded to the intervention. Masked infusion bags of 0.8% lidocaine or normal saline will be prepared by the investigational pharmacy at University of Missouri Hospital. To avoid any compromise in the blinding process, the investigational pharmacist will enter "Study Medication" in the medical record.

Perioperative care, surgery and anesthesia, for all subjects will be per standard hospital protocol.

In short:

Upon arrival to the operating room, patients will be placed supine on the operating table and intravenous (IV) lines connected to allow initiation of IV lidocaine or saline following anesthetic induction. IV antibiotics will be utilized if clinical necessary based on the discretion of the anesthesiologist and attending surgeon. Standard perioperative monitoring including a

continuous electrocardiogram, pulse oximetry, urine output, non-invasive arterial pressure measurement, end-tidal CO₂ and temperature will be utilized. Intravenous fluid use during surgery will be provided by the anesthesiology team as clinically indicated. Anesthesia will be standardized. Induction will be with lidocaine 1.5 mg/kg, fentanyl 1 mcg/kg, propofol 1.5 to 2 mg/kg, and rocuronium 0.6 mg/kg. Patient will then be prepared and draped in sterile fashion. Timeout will be performed.

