Anesthesia will be maintained with 1 MAC sevoflurane, additional fentanyl and rocuronium will be given per anesthesia discretion. Quantity of all anesthetic and analgesic medications during the operation will be documented. Local 0.25% bupivacaine (10mL) without epinephrine injection will be used post-operatively during closure in all patients regardless of being in the study group or control group as a part of normal operational procedure. Reversal of neuromuscular blockade will be with sugammadex 2 mg/kg. When standard extubation criteria are met the subject will be extubated and transported to PACU.

Intervention

Fifteen minutes following endotracheal intubation, subjects will be intravenously infused with either 0.8% lidocaine at 1 mg/kg/h if < age 65 and 0.5 mg/kg/h if ≥ age 65 or an equal volume and rate of normal saline placebo as determined by the randomization table. The infusion will be continued for 24 hours after surgery. Masked infusion bags of 0.8% lidocaine or normal saline will be prepared by the Investigational Pharmacy at the University of Missouri Hospital according to the subject randomization table. Infusion preparation will occur in a blinded fashion to all clinical and research personal involved with the study case. To maintain blinding, the investigational pharmacist will enter "Study Medication" in the medical record.

In PACU patient will receive additional fentanyl or hydromorphone. Postoperative pain scores, vital measures, and opioid use will be documented. Once patient is able to tolerate oral intake, they will be switched to oral narcotics. Patient fentanyl consumption and 10 cm visual analog scale (VAS) will be utilized. VAS will be scored from a 0 "no pain" to a 10 "worst pain ever" and will be recorded by blinded research staff at 1, 2, 4, 6, 12, 24 hours post-operatively, postop day 2, any additional day during hospitalization, at time of discharge and 14-day follow up. The nurse that will be caring for these patients will document the time of first bowel movement, return of flatus and any adverse reactions per standard of care. Post-Anesthesia Patient Satisfaction Assessment will be performed at 24 h post-surgery.

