This study does not require any additional pretreatment evaluations other than those which are part of current clinical care standards for a patient undergoing RALP or RALPN at University of Missouri. Preoperative evaluations follow recommendations from the NICE^{34,35}.

For RALP these include:

- Routine history and physical examination to include documentation of any comorbidities, medications (including complementary and alternative medications), family history, social history (alcohol and tobacco usage), height, body weight, Karnofsky performance status within 30 days of surgery
- Chest X-ray or CT scan of the Chest within 30 days of surgery
- Pre-operative laboratory investigations: CBC, BMP, urinalysis (dipstick, microalbumin, creatinine, microscopic evaluation if indicated), urine culture if indicated within 30 days of surgery
- Baseline EKG

For RALPN these include:

- Routine history and physical examination to include documentation of any comorbidities, medications (including complementary and alternative medications), family history, social history (alcohol and tobacco usage), height, body weight, Karnofsky performance status within 30 days of surgery

- Abdominal and pelvic CT scan and/or MRI and/or renal ultrasound within 60 days of surgery.
- Chest X-ray or CT scan of the Chest within 30 days of surgery
- Pre-operative laboratory investigations: CBC, BMP, urinalysis (dipstick, microalbumin, creatinine, microscopic evaluation if indicated), urine culture if indicated within 30 days of surgery
- Baseline creatinine values will be converted to eGFR using the CKD-EPI equation
 - o This value will be recorded from the MU pre-surgical testing blood work mandatory for all patients undergoing surgery at MU.

SURGICAL INTERVENTION PLAN

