Surgical complications will be assessed prospectively and retrospectively and reviewed using the institutional standard for complications reporting for all surgical patients as followed by the Department of Surgery. Standardized graded complications and adverse effects at UM utilize the five-point modified Clavien-Dindo system. Grade I include complications requiring monitoring but no intervention; Grade II requires bedside or medical treatment; Grade III constitute adverse events requiring surgical or procedural intervention with return to normal functioning; Grade IV includes disabling, life-threatening complications with resulting functional loss and grade V is death of the patient. This is a modification of the Clavien-Dindo system for reporting complications with defined, categorized and classified events that will be segregated into time periods of ≤ 30 days, 31-90 days and > 90 days after surgery and includes medication complications following NCI CTCAE version 5 guidelines.

CRITERIA FOR THERAPEUTIC RESPONSE/OUTCOME ASSESSMENT

If the surgery is aborted for any reason before attempted excision of the mass or intravenous infusion fails for any reason, the patient will be removed from the study and replaced. Based on past experience these issues are rare events. If a partial nephrectomy converts to radical nephrectomy, infusion will be continued and the data will be collected. If any robotic procedure converts to an open procedure, the subject will be excluded from the study. Lidocaine infusion will be continued or started (if subject is receiving normal saline) per surgeon request.

The intraoperative period is defined as the period from anesthesia induction to the extubation of the trachea. The surgical time is determined from the incision to the final skin closure.

The postoperative period is defined as the period from the extubation to the study endpoint at 14 days \pm 7 days.

Blood loss is defined as the estimate accounted from the suction device and absorptive sponges during the procedure, as described and agreed upon by the surgeon, anesthesiologist, circulating nurse, and surgical technician as covered by institutional guidelines.

Post-operative pain will be defined by the patient through the use of a 10 cm visual analog scale (VAS) and 11 point numeric scale (0-10).

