Length of hospital stay will be defined as the time the subject leaves the OR until subject meets standardized discharge criteria according to the surgeons' protocol, which will exclude social factors delaying real discharge times.

Post-operative ileus duration is defined as return of bowel function in hours from extubation per patients recall following nursing inquiry. Documentation will be done per standard of care by the nurse caring for study patient.

Flatus return is defined as return of flatus in hours from extubation per patients recall following nursing inquiry. Documentation will be done by nurse caring for patient following standard of care.

Patient satisfaction will be assessed 24 hours post-operative by Post Anesthesia Patient Satisfaction Assessment by research staff.

CRITERIA FOR REMOVAL FROM STUDY

Patients will be withdrawn from the study if they express a desire to do so, if it is determined to be in the patient's best interest to do so, or if they do not undergo initiation of their surgical procedure as stipulated previously. If lidocaine infusion is stopped subject will be excluded from analysis. If surgery is converted from robotic assisted to open the subject will be excluded from analysis. Patients who are not evaluable for the study primary endpoint by failure to obtain

data for the primary endpoint will be excluded from the study and further analysis will not be performed.

BIOSTATISTICS

Sample Size

The primary outcome for the study is the patient's pain score at discharge. Although additional analyses are planned, the sample size estimate is based on this outcome. Assuming a common standard deviation of two-points, a sample size of 40 with 20 per treatment arm will provide 80% power to detect a 2-point difference between groups when testing a two-sided alternative at the 5% level of significance using Wilcoxon Rank Sum Test. To take into account the loss to follow up, the drop-out inflated enrollment will be 46 subject with 23 subjects in each group assuming the same power.

Unadjusted and Adjusted Analysis

The unadjusted analysis will be designated as primary analysis and it will be performed to assess the pain level difference between the two groups. The adjusted analysis which will be designated as secondary analysis will incorporate other covariates like type of surgery in addition to the treatment assignments as covariate.

Proposed Analyses

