Two statistical analysis methods will be used to make a comparison between the two treatment groups with regard to the primary end point: (i) to assess the difference of pain level between the two groups at specific time point, Wilcoxon Rank Sum Test will be used, (ii) to assess the pattern of change in pain level over the study period between the two groups, a Generalized Estimation Equation (GEE) model will be used.

Sample Size					Drop-out Inflated Enrollment	
Treatment	Placebo	Effect Size	SD	Power	Treatment	Placebo
20	20	2	2	80%	23	23
27	27	2	2	90%	30	30

*A dropout rate of 10% was considered here. A Two Sample T-test using effect size sample size method was used to get an estimate of the samples needed from the PASS program.

Table 2: Sample size assuming 80% and 90% power.

RESEARCH PARTICIPANT REGISTRATION AND RANDOMIZATION PROCEDURES

Research Participant Registration

Confirm eligibility as defined in the section entitled Criteria for Patient/Subject Eligibility.

Obtain informed consent, by following procedures defined in section entitled Informed Consent Procedures.

Randomization

Randomization will be accomplished by the method of random permuted block and stratified by the type of the surgery and subject age. Since this is a double-blind study, the subjects' treatment assignments will be kept in a blinded randomization table. The Excel column containing treatment designation assigned by a biostatistician will be occluded from view to maintain blinding. The investigational pharmacist will not be blinded and will have the randomization table. After recruitment, research staff will randomize the patient into the correct stratification and the Investigation Pharmacy will be notified. If it is clinically necessary to unblind a subjects' treatment allocation this will be done using the randomization table.

DATA MANAGEMENT ISSUES

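### No pain score is planned before treatment, so the secondary adjusted analysis and the GEE cannot adjust for existing pain

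*Combined protocol and SAP*

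**What the plan says.** **Timing of pain scores (Overview of Study Designation, Intervention).** The VAS "will be recorded by blinded research staff at 1, 2, 4, 6, 12, 24 hours post-operatively", and then on "postop day 2, any additional day during hospitalization, at time of discharge and 14-day follow up". The PACU scores in the same section and the VAS at the follow-up appointment are post-operative too.

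**Start of treatment (Overview of Study Designation, Design).** "The infusion will be started 15 minutes after endotracheal intubation and continue for 24 hours". The first scheduled score therefore comes after the infusion has begun.

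**Before surgery (Pretreatment Evaluation).** "This study does not require any additional pretreatment evaluations other than those which are part of current clinical care standards". The lists for prostatectomy and for partial nephrectomy contain no pain score. After admission, the section on evaluation during treatment adds only the satisfaction inquiry and toxicity monitoring to routine care. The outcome section defines post-operative pain only.

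**Analyses (Biostatistics).** The unadjusted comparison is primary. The adjusted analysis is secondary and "will incorporate other covariates like type of surgery in addition to the treatment assignments as covariate". A GEE is to be used "to assess the pattern of change in pain level over the study period between the two groups". No baseline term or reference time is given for it.

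**The concern.** The outcome is a subjective score in a small trial, and two planned secondary analyses could make use of a pre-treatment value of that score. The covariate list of the adjusted analysis is open-ended, but preoperative pain can never join it because nobody is scheduled to collect it. The GEE has no pre-treatment starting point.

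Preoperative pain need not be zero in everyone. The eligibility criteria exclude current opioid users and patients with documented opioid abuse, but not patients who have pain and take no opioid. With about 20 per arm, the groups could differ in existing pain by chance. The trial could not show this in its baseline table or adjust for it directly, and the score cannot be taken after the event.

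At stake are some precision in the secondary analyses and the ability to answer a reader who asks whether the arms started level.

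**Working it through.** **1. The plan's own sample size.** The inputs from Biostatistics are a difference of 2 points, SD 2, two-sided 5%, and 20 per arm for 80% power or 27 for 90%.
- An exact two-sample t-test needs 17 and 23 per arm.
- Dividing by 0.864, the minimum asymptotic relative efficiency of the Wilcoxon test, gives 17/0.864 = 19.7 → 20 and 23/0.864 = 26.6 → 27.
- With 10% dropout, 20/0.9 = 22.2 → 23 and 27/0.9 = 30.

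The stated figures reproduce. The Wilcoxon allowance is not written in the plan and is inferred from the match. None of this uses a baseline score, so the planned size does not depend on one.

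**2. Assumption.** The documents give no correlation r between preoperative and discharge pain. A range of 0.1 to 0.5 is used.

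**3. How far chance imbalance can move the result.** An imbalance in preoperative pain reaches the discharge comparison only through the regression slope, r × SD(outcome)/SD(baseline). The baseline SD cancels, which leaves a 95% limit of

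1.96 × r × 2 × √(2/20) = 1.24 × r

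| r | 95% limit of shift (points) |
|---|---|
| 0.2 | 0.25 |
| 0.3 | 0.37 |
| 0.5 | 0.62 |

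The design target is 2 points.

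**4. Power of the adjusted comparison, t-test basis, 20 per arm.**
- Without a baseline: SE = 2 × √(2/20) = 0.632, noncentrality 2/0.632 = 3.16, 38 degrees of freedom, power 86.9%. This exceeds the stated 80% because 20 per arm includes the Wilcoxon allowance.
- With a baseline covariate: residual SD = 2 × √(1 − r²), 37 degrees of freedom, and variance multiplied by 1 + 1/36 for the expected covariate imbalance.

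| r | Residual SD | SE | Power |
|---|---|---|---|
| none used | 2.00 | 0.632 | 86.9% |
| 0 | 2.00 | 0.641 | 85.9% |
| 0.1 | 1.99 | 0.638 | 86.3% |
| 0.2 | 1.96 | 0.628 | 87.3% |
| 0.3 | 1.91 | 0.612 | 89.0% |
| 0.5 | 1.73 | 0.555 | 93.9% |

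Adjustment costs about 1 percentage point of power if r is 0, breaks even near r = 0.17, and gains about 7 points at r = 0.5.

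**The case against.** The strongest reply is that nothing the trial depends on is affected. The primary analysis compares randomized groups without adjustment and is valid with no baseline. Chance variation in preoperative pain is already part of that test's standard error, so it is not bias. This stands in full.

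A reader might infer that the GEE will treat the 1-hour score as baseline and so subtract out an early lidocaine effect. The documents do not support that. They refer to change over the study period, never to change from baseline, and no section gives the 1-hour score that role. In a GEE fitted to the post-operative scores, an early effect would sit in the treatment main effect. What remains is that the plan does not say how the pattern is to be read.

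A reader might also set the possible imbalance in the preoperative score directly against the 2-point target. If that score had an SD of 1 to 2 (an assumption), the 95% limit would be 1.96 × SD × √(2/20), or 0.62 to 1.24 points. But the target is a difference in discharge pain. Only the part carried by r reaches it, and the whole 1.24 would need r = 1.

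A low r is plausible. Current opioid users are excluded, and pain at discharge follows surgery, local bupivacaine and opioids. Comorbidities and home medications are recorded, so analgesic use offers a partial proxy. Routine care may also record a preoperative pain score, but the documents do not say so and do not plan to collect or use one. These points lower the likely gain without removing the gap.

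**Conclusion.** The point holds as a low-cost improvement to the secondary analyses. No pre-treatment pain score is planned, so neither the adjusted analysis nor the GEE can adjust for existing pain, and an imbalance in it cannot be reported. It is not a flaw in the primary Wilcoxon comparison or in the sample size, and it does not invalidate the GEE as a description of the post-operative course.

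The size is small to moderate and depends on an assumed r. At r = 0.2 to 0.5, chance imbalance shifts the discharge difference by at most about 0.25 to 0.62 points (95% limit), and adjustment adds about 0.4 to 7 percentage points of power. If most patients score 0 before surgery there is no gain, and up to about 1 point of power is lost. The calculation takes the plan's SD of 2 and 20 evaluable patients per arm, and it assumes approximately normal scores and a linear relation between preoperative and discharge pain.

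**What to change.** - Add one preoperative VAS to the schedule in the Intervention section. Use the same 10 cm scale, taken by research staff on the day of surgery before induction. Induction is the right cut-off because the standard induction includes lidocaine for all patients.
- Name the score as a covariate in the secondary adjusted analysis and in the GEE, with post-operative scores as the outcomes. State that the 1-hour score is an outcome and not a baseline.
- Report the preoperative score by arm in the baseline table.
- Keep the unadjusted Wilcoxon test as the primary analysis.
- If patients have already been operated on without the score, state that the GEE describes the post-operative course only.

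The cost is one question asked by staff already assigned to record the VAS, a one-line change to the protocol and the data collection form, one model degree of freedom and some missing baseline values. Treatment, randomization and sample size do not change.
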